6.4 Method of Assigning Patients to Treatment

Interactive response technology (IRT) will be used in this study. Each patient will be assigned a screening number, and that number will be used to identify the patient throughout the study. When a patient is to be randomized, the unblinded pharmacist or designee will use the IRT. The IRT will allocate the patient to a treatment group during the call and assigns the patient a randomization number in accordance with the specifications from Biostatistics, H. Lundbeck A/S.

6.5 **IMP Accountability**

IMP accountability will be documented in the IRT by the unblinded CRA.

The investigator and the pharmacist must agree to only dispense IMP to patients enrolled in the study. The pharmacist must maintain an adequate record of the receipt and distribution of the IMP(s). This record must be available for inspection at any time.

6.6 Unblinding Procedures

Pharmacovigilance, H. Lundbeck A/S, and the investigator or the pharmacist (if applicable), and the DMC will have access to the unblinded information for the double-blind treatment for each patient. Access to these details will be via IRT.

The IRT unblinding procedure is described in the IRT User Guide.

The investigator may only break the code for a patient if knowledge of the IMP is necessary to provide optimal treatment to the patient in an emergency situation. If possible, the investigator must consult the CRA in some cases it may be the medical monitor before breaking the code. The investigator must record the date and reason for breaking the code on the *IMP Code Break Form*. If the emergency situation was an adverse event, it must be recorded on an *Adverse Event Form*. The CRA (in some cases it may be the medical monitor) must be notified immediately. The IRT will capture the date and time of the code break call. Information on the allocated treatment will be provided during the call and by fax or email, depending on availability/preference. When the code is broken for a patient, the patient must be immediately withdrawn from the study. If this occurs during a visit, the investigator must

complete the visit as a Withdrawal Visit; otherwise, the patient will be asked to attend a Withdrawal Visit 12 weeks after his/her last dose of IMP.

6.7 **Post-study Access to IMP(s)**

Patients in the study will have access to appropriate medical care after they complete or withdraw from the study.

7 Concomitant Medication

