- r An unblinded pharmacist or designee is responsible for receiving, storing and preparing IMP. The pharmacist or designee will not be responsible for other aspects of the clinical trial where blinding is necessary.
- s A designated unblinded CRA is responsible for the IMP accountability.
- t Pregnancy test at Screening to be performed using serum β -HCG. At all other visits, urine pregnancy testing will be performed and in case of a positive finding, confirmatory testing will be performed via serum β -HCG.
- u Exit Interview subset: Patients undergoing the exit interviews must provide signed subset-specific Informed Consent. The exit interview will be conducted shortly (no later than 2 weeks) after the last assessment of the Week 24 Visit or Withdrawal Visit for patients who withdraw prior to Week 24. The exit interview must be conducted after all visit assessments are completed. Details will be provided in a separate exit interview guide.
- v Patients who withdraw, except for those who withdraw their consent, will be asked to attend a Withdrawal Visit 12 weeks after the last dose of IMP and undergo Safety Follow-Up evaluations. Patients who withdraw prior to Week 24 will undergo additional Efficacy Follow-Up evaluations.
- w Exploratory gene expression profiling (RNA) and metabolomics/proteomics are an integrated part of the study and are covered by the main Informed Consent.
- x Sampling for pharmacogenetics is optional and a separate signed Informed Consent must be in place to cover this analysis.
- y Whole blood samples for serum separation and potential future ADA analyses will be drawn at Week 24 and at the Completion or Withdrawal Visit.

Table of Contents

List	of Pan	els	22
List	of Abb	previations and Definitions of Terms	23
Mai	or Cha	nges Since Last Edition	26
1		luction	
	1.1	Background	30
		1.1.1 Overview	30

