Patients will be assigned a headache eDiary at the Screening Visit and will be required to complete this daily from the time of screening until the Completion/Withdrawal Visit. During infusion visits, assessments of safety will be performed before and after each infusion. At these visits, AEs will be collected as well as safety laboratory tests, ECG, weight, and vital signs. Patient-reported outcomes (PROs) must be completed prior to infusion.

Patients who complete the study will attend a Completion Visit which will include a Safety Follow-up evaluation at 12 weeks after their last dose of IMP.

Patients who withdraw, except for those who withdraw their consent, will be asked to attend a Withdrawal Visit 12 weeks after their last dose of IMP which will include Safety Follow-Up evaluations. Patients who withdraw prior to the Week 24 Visit will additionally undergo Efficacy Follow-Up evaluations.

Patients in the study will have access to appropriate medical care in accordance with normal clinical practice after they complete or withdraw from the study.

An independent Safety Data Monitoring Committee (DMC) will regularly monitor the patients' safety data according to the DMC Charter.

In general, no information about individual treatment codes will be available to investigators patients or site-facing CRO personnel (blinded team) until after the last patient has completed the study.

The results of the Placebo-controlled Period will be reported on when ended for all patients. All data from the Placebo-controlled Period will be cleaned and the database for the Placebocontrolled Period will be locked. Data will be unblinded for the reporting team (Sponsor) and all analyses specified in the SAP for data collected in the Placebo-controlled Period will be performed and included in the Clinical Study Report (CSR). After all patients have completed the study, an addendum to the CSR, including the results from the Extension Period, will be produced. Investigators and patients will be informed about which treatment (active or placebo) their patients received in the Placebo-controlled Period and the actual dose of eptinezumab received in the Extension period only after the last patient has completed the study.

Assessments performed in a subset of patients:

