8.9 Withdrawal Visit

Patients who withdraw from the study will be asked to attend a Withdrawal Visit, if at all possible. The visit must be scheduled 12 for weeks after the last dose of IMP after withdrawal.

As the Withdrawal Visit will be scheduled 12 weeks after the last dose of IMP, this visit will also serve as a Safety Follow-up Visit for all withdrawn patients (section 8.10). Patients who withdraw prior to Week 24 will undergo additional efficacy evaluations, thus for these patients the Withdrawal Visit will also serve as an Efficacy Follow-up Visit.

At the Withdrawal Visit, the patient must be assisted with the closeout of the eDiary.

No new information will be collected from patients who withdraw from the study, except information collected in relation to the scheduled Withdrawal Visit or needed for the follow-up of adverse events (section 10.5).

The reason for withdrawal must be recorded in the eCRF.

For a patient who withdraws consent:

- if the patient withdraws consent during a visit and then agrees to it being the final visit, the investigator will complete the visit as a Withdrawal Visit and all the data collected up to and including that visit will be used
- if the patient withdraws consent during a telephone conversation, the investigator will ask the patient if they will attend a Withdrawal Visit 12 weeks after their last dose. If the patient:
 - agrees to attend a Withdrawal Visit, all the data collected up to and including that visit will be used
 - refuses to attend a Withdrawal Visit, the investigator should attempt to follow the patient's safety and future treatment; any information collected will only be recorded in the patient's medical records
- if the patient explicitly requests that the patient's data collected from the time of withdrawal of consent onwards not be used, this will be respected

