8.10 Safety Follow-up at Completion or Withdrawal Visit

As the Completion or Withdrawal Visit will be scheduled 12 weeks after the last dose of IMP, these visits will also serve as Safety Follow-up Visits.

A safety follow-up is conducted to capture adverse events that occur after the last IMP or Phone Contact Visit (whichever is later) as well as to follow up on the outcome of adverse events ongoing at that visit at the Completion/Withdrawal Visit.

For adverse events that were ongoing at the last IMP or Phone Contact Visit and that resolved by the Completion/Withdrawal Visit, the stop date must be recorded. For non-serious adverse events still ongoing at the Completion/Withdrawal Visits, the *Ongoing Adverse Event* checkbox on the *Adverse Event Form* must be ticked. SAEs must be followed until resolution or the outcome is known.

For patients with a clinically significant out-of-range clinical safety laboratory test value at the Completion or Withdrawal Visit or who withdrew due to an elevated AST or ALT value (see section 5.4), safety follow-up should be scheduled and recorded in the patients' medical records and not in the eCRF; see section 10.5 for details.

The safety follow-up for patients who withdraw consent must be performed, if at all possible; any information collected will be recorded in the patients' medical records.

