The patient will receive IMP starting from the Baseline Visit to follow a dosing schedule with IV infusions every 12 weeks with either eptinezumab or placebo over 30 minutes (+15).

At Visit 8 patients will enter the Extension Period. Patients who were assigned to placebo in the Placebo-controlled Period will be randomly allocated to one of two treatment groups: eptinezumab 300 mg or eptinezumab 100 mg with a ratio of 1:1. Patients assigned to eptinezumab 300 mg or eptinezumab 100 mg in the Placebo-controlled Period will continue on their original assignments.

An overview of the study is presented in Panel 2 and the scheduled study procedures and assessments are summarized in Appendix II. See also the *Clinical Study Protocol* for further details on the study design.

Panel 2 Study Design

For patients who withdraw, except for those who withdraw their consent, a Withdrawal Visit will be scheduled 12 weeks after the last dose of IMP. The withdrawal visit will include Safety Follow-up evaluations and will therefore also serve as a Safety Follow-up Visit.

For patients who withdraw prior to Week 24 the Withdrawal Visit will allow for eDiary closeout and for a final assessment of scales not based on the eDiary. Patients are expected to complete their eDiary until this Withdrawal Visit unless the patient withdraws consent.

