19.2.1 Clinical Outcome Assessments (COAs) - Scales

For treated patients withdrawing prior to Week 24, the withdrawal visit scheduled 12 weeks after the last IMP infusion will also include efficacy evaluations (PGIC, MBS, HIT-6, MSQ, EQ-5D-5L, HCRU, and WPAI:M). These assessments will be assigned to either Visit 5 or Visit 8 according to when the patient was withdrawn as follows:

- For patients withdrawing prior to Visit 5, the assessments from the Withdrawal Visit will be assigned to nominal Visit 5
- For patients withdrawing after Visit 5 (but prior to Visit 8), the assessments from the Withdrawal Visit will be assigned to nominal Visit 8.

Unscheduled visits will not contain assessments of the COAs mentioned above. In relation to the nominal visits post-Baseline, a patient can complete their COAs 3 days before the visit. In case of duplicate scale assessments in relation to a nominal visit, i.e. if a patient fills out the scales 3 days before the visit and the visit is postponed afterwards implying that the patient has to complete the COA again, the latest assessment will be used.

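### Protocol 6.6 makes a visit with a code break the Withdrawal Visit, so a break after that day's infusion has started puts the safety follow-up on day 0 instead of day 84 after the dose

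*Protocol*

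**What the plan says.** Protocol 6.6 allows a code break only when knowing the treatment is needed for emergency care, and requires immediate withdrawal afterwards. For a break that happens while the patient is at a visit, the instruction is to "complete the visit as a Withdrawal Visit; otherwise, the patient will be asked to attend". The remainder of that sentence puts the alternative, later visit at 12 weeks from the most recent infusion.

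The other places that set the timing do not mention a code break or refer to 6.6:

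- Protocol 3.1, on withdrawn patients: "except for those who withdraw their consent, will be asked to attend a Withdrawal Visit 12 weeks after their last dose of IMP".
- Panel 2 footnote v: such patients "will be asked to attend a Withdrawal Visit 12 weeks after the last dose of IMP and undergo Safety Follow-Up evaluations", again except those who withdraw consent.
- Protocol 8.9: "The visit must be scheduled 12 for weeks after the last dose of IMP after withdrawal" (word order as in the protocol). Its only route to a same-visit Withdrawal Visit is a patient who withdraws consent during a visit.
- Protocol 8.10: because the Completion or Withdrawal Visit falls 12 weeks after the last dose, "these visits will also serve as Safety Follow-up Visits".

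On data after withdrawal, 8.9 says: "No new information will be collected from patients who withdraw from the study, except information collected in relation to the scheduled Withdrawal Visit". The sentence goes on to except information needed to follow up adverse events under 10.5. For patients who withdraw before Week 24, SAP section 2 adds: "Patients are expected to complete their eDiary until this Withdrawal Visit unless the patient withdraws consent".

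**The concern.** The 12-week interval is what makes the Withdrawal Visit usable as a safety follow-up; 8.10 gives it as the reason. A severe reaction during an infusion, or in the observation hour after it, is an obvious emergency in which a code might be broken, and the patient is then still at a visit. Followed as written, 6.6 makes that day's visit the last scheduled contact, although the patient has just been exposed to the dose.

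At stake is the scheduled safety information for that dose in a small group chosen because something went wrong. The protocol lists safety and long-term safety as objectives.

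**Working it through.** **The interval.** 12 weeks × 7 = 84 days, which matches the nominal day for Visit 5 (Week 12) in SAP Panel 10.

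**Days from last dose to Withdrawal Visit if 6.6 is followed.** The shortfall is 84 minus the days since the last dose.

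- Infusion visit, after that day's infusion has started: day 0, so 84 − 0 = 84 days short.
- Infusion visit, before that day's infusion (Visits 5, 8, 11, 14, 17): about day 84, so little or no shortfall.
- Phone contact 4 or 8 weeks after a dose, if counted as a visit: day 28 or 56, so 56 or 28 days short. No loss is claimed here. The Withdrawal Visit needs on-site procedures, so the natural reading is that the 12-week visit is kept.

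**What a day-0 Withdrawal Visit leaves out.**

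- *Assessments.* Panel 2 footnotes n and o place laboratory samples, ADA, ECG, physical examination and C-SSRS before the infusion. Only adverse events and vital signs are also checked after it. The set filed as the Withdrawal Visit would therefore largely predate the dose it should follow up, and the 12-week set is not done.
- *Adverse events.* Protocol 10.5 ends follow-up of non-serious events at resolution or at the Withdrawal Visit, whichever comes first. New non-serious events after day 0 have no scheduled query. SAP Appendix VI, Table 6 counts angioedema/urticaria, infusion site reactions, pruritus and rashes as infusion-related events of special interest for up to 7 days after dosing. That window would be almost wholly unqueried.
- *eDiary, before Week 24.* Closeout takes place at the Withdrawal Visit (8.9, footnote j, SAP section 2). Closing on day 0 loses 84 / 28 = 3 four-week MMD values per affected patient: Weeks 1-12 after a break at Visit 2, or Weeks 13-24 after a break at Visit 5.

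**What continues.** The exception in 8.9 leaves room for follow-up of adverse events under 10.5. SAEs are followed until the patient has recovered, stabilized or recovered with sequelae, and SAEs reported spontaneously later are handled as in-study SAEs (10.5). Clinically significant laboratory values are followed in usual practice (10.5). Immune-response samples can be taken at the time of the event (10.6).

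**How many patients.** The documents give no code-break rate, so the following are assumptions. If 0 to 1% of 840 patients have a code break: 840 × 0 = 0 to 840 × 0.01 = 8.4. If 10 to 50% of those follow infusion start on a dosing day: 0 × 0.10 = 0 to 8.4 × 0.50 = 4.2 patients over the whole study.

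**The case against.** The best reply is that 6.6 is a deliberate exception. It is the only section on visit timing after a code break, it restates the 12-week rule for every other case, and a specific rule ordinarily governs a general one. Section 8.9 is also softer than its mandatory sentence suggests: patients are asked to attend if at all possible, and a same-visit Withdrawal Visit is accepted when consent is withdrawn. So the documents do not establish an irreconcilable contradiction. This part of the reply stands, but it does not remove the problem. If 6.6 prevails, the safety follow-up is on day 0, and the reason 8.10 gives for letting the visit serve as one no longer applies.

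The case is also rare. There is no specific antidote, and emergencies are treated by standard care (10.6), so unblinding will seldom be needed. In the Extension Period every patient receives eptinezumab, so knowing the current treatment reveals only the dose. This stands too and limits the weight of the point.

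A reader might infer two stronger things that the documents do not support:

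- *That dosing-day HIT-6 and other scale values would be analysed as Week 12 or Week 24 values.* SAP 19.2.1 does say "For patients withdrawing prior to Visit 5, the assessments from the Withdrawal Visit will be assigned to nominal Visit 5", with a parallel rule for Visit 8. Its opening sentence, however, concerns the withdrawal visit scheduled 12 weeks after the last infusion, and a day-0 visit is outside that. At Visit 2, scales completed before the infusion also meet the baseline definition in SAP 4.2. No misassignment is claimed.
- *That the reaction prompting the break goes unfollowed.* An anaphylactic reaction would normally be an SAE, and SAEs are followed to outcome with or without a code break. What is lost is the scheduled search for other, non-serious events and one set of assessments.

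**Conclusion.** The point holds as a minor, cheaply corrected weakness in safety follow-up. It depends on two conditions: the code is broken after that day's infusion has started, and the site follows 6.6 rather than 8.9. Per affected patient, the follow-up comes 84 days early, with one adverse event query and one assessment set not done. Before Week 24, three four-week MMD values are also not collected. On the assumed rates this concerns 0 to about 4 patients, and zero is plausible. With numbers this small, the effect on the efficacy estimates is negligible.

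**What to change.** Amend 6.6: after a code break at a visit less than 12 weeks after the last dose, including one where that day's infusion has started, the investigator completes that visit's assessments, gives no further IMP, and still asks the patient to attend the Withdrawal/Safety Follow-up Visit 12 weeks after the last dose. Adverse events are collected until then.

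The cost is one sentence and at most one extra visit, already standard for other withdrawn patients, for a handful of patients. No SAP change is needed, because the withdrawal listing in SAP 7.2 already flags a broken code and so identifies any case. Edition 3.0 postdates completion of the Placebo-controlled Period, so the change can act only on extension visits; any eDiary data already lost before Week 24 cannot be recovered by it.

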7.1 General

Concomitant medication is any medication other than the IMP that is taken during the study up until the Completion/Withdrawal Visit, including during the Screening Period.

The concomitant medications that are disallowed or allowed with restrictions during the study are summarized in Appendix II.

Details of all concomitant medication (prescription and over-the-counter) taken <3 months prior to the Screening Visit must be recorded in the eCRF at the first visit. Any changes (including reason for changes) in concomitant medication must be recorded at each subsequent visit.

Details of all migraine preventive treatment failures (prescription and over-the-counter) taken ≤ 10 years prior to the Screening Visit must be recorded in the eCRF at the Screening Visit.

For any concomitant medication for which the dose has been increased due to worsening of a concurrent disorder after enrolment in the study, the worsening of the disorder must be recorded as an adverse event.

For any concomitant medication initiated due to a new disorder after enrolment in the study, the disorder must be recorded as an adverse event.

7.2 Use of Coronavirus Disease 2019 Vaccine

There are currently no data indicating that eptinezumab interacts with or impairs the body's immunological response to the COVID-19 vaccines. Hence, there are no indications for safety concerns of concomitant use of the COVID-19 vaccines with eptinezumab. As such, COVID-19 vaccination is allowed during the eptinezumab studies with the guidance measures described in Appendix II. All adverse events, including those judged by the investigator to be related to the COVID-19 vaccine, must be recorded in the eCRF (see section 10.1.1). A causality assessment, including an alternative causality as relevant, must be provided.

8 Study Visit Plan

8.1 Overview

An overview of the procedures and assessments to be conducted during the study and their timing is presented in Panel 2. Further details are in chapter 9.

The Screening Visit (Visit 1) is performed 28 to 30 days before the Baseline Visit (Visit 2).

Thereafter, study visits are divided into Phone Contacts and IMP Visits. The Primary Outcome Visit (Visit 5) is performed 12 weeks after the Baseline Visit. Patients will continue until the Completion Visit (Visit 20) or until the Withdrawal Visit.

At Visit 8 patients will enter the Extension Period and receive either one of two treatments: eptinezumab 300 mg or eptinezumab 100 mg until the Completion Visit (Visit 20).

Patients will complete a daily headache eDiary from the time of screening until the Completion/Withdrawal Visit. Patients will be given a headache eDiary at the Screening Visit and must be trained in its use and compliance requirements. Patients will complete electronic headache diary entries daily. At each clinic visit and phone contact (that is every 4 weeks), a compliance check of the eDiary will be conducted. Patients must continue to complete the daily eDiary during the transfer to the Extension Period. Headache data from the eDiary will be made available during the study to site staff for review via the eDiary system portal. See section 9.2.2 for further details on eDiary.

All assessments may be completed over a maximum of 2 consecutive days (with the exception of PROs - see below); if so, the first day is considered the "visit" day according to the schedule. If the date of a clinic visit or phone contact does not conform to the schedule, subsequent visits should be planned to maintain the visit schedule relative to the Baseline Visit.

PROs which are scheduled in alignment with a clinic visit can be completed in the clinic or in the remote setting within 3 days prior to the scheduled clinic visit date. PROs which are scheduled in alignment with a phone contact (PGIC (at Week 4 only), HIT-6, EQ-5D-5L, HCRU, WPAI) must be completed in the remote setting and can be completed on the day or within 3 days prior to the scheduled phone contact date.

After completing or withdrawing from the study, the patient must be treated in accordance with usual clinical practice.

